3.4.1 Inclusion Criteria

- 1) Aged 5 through 12 years old
- 2) Receiving ADHD treatment from participating practices
- 3) ADHD or ADD diagnosis code, ICD-10-CM F90.9 or F90.0, listed in the problem list or recorded at an ambulatory visit in the past year.
- 4) Parental/guardian permission (informed consent) and if appropriate, child assent.

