5.5 Sample Size and [name]

Aim 1: The investigative team assumed that there will be 240 evaluable children parent-child dyads (from 300 enrolled), and that these will be divided 1:1 across the two groups. From these assumptions, power analyses we conducted based on simulations, in which two groups of 120 children were generated, followed over 3 time periods (totaling 9-12 months), where the measurements were correlated from baseline to 6-8 months (corr=0.8) and from baseline to 9-12 months (r=0.6). The investigative team assumed that the true differences between treatment groups was a score of 5.0 units over time. Once a dataset was simulated, a marginal model for longitudinal data was applied (GEE with a first order auto-regressive working correlation structure and robust variance estimates). For comparing the effect of the intervention, power of 0.87 was found to detect a difference of 2.5 points along the Vanderbilt score (assuming a standard deviation of 6 points, and a difference of 2 points assuming a standard deviation of 5). These good levels of power are achievable with the longitudinal design.

Aim 2: For the outcomes of initiation and adherence, binary outcomes were assumed and performed analyses using the PASS 13 software (Hintze, 2011). For the purposes of this study, the ADHD PGI will be used to determine the level of initiation and adherence. Initiation is defined as starting a treatment plan for which one has moderate to greater preference. Adherence is defined as the continuation of treatment through month 9-12. Assuming that the tier 1 group of 120 children experiences a 50% rate of initiation and adherence, power would be about 0.89 to detect an increase in that rate among the tier 2 group to 70% and would be greater than 0.98 to detect an increase to 75%.

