
We conducted sensitivity analyses to examine the impact of preference and treatment intensity on the main outcome of ADHD symptoms. We stratified tier 2 participants by intervention dosage (frequency of interaction with the portal/care manager): 0-1 sessions, 2 sessions, or 3 or more sessions. We compared differences in ADHD symptom score changes over time by intervention dosage using a linear mixed effects model that adjusted for seasonality.

Aim #2: We originally proposed to assess whether family engagement, treatment initiation and adherence were mediators of intervention treatment effects: This analysis proposed to focus on the role of engagement and treatment initiation at 3 months or adherence at 6 and 9 months as mediators of the effect of the intervention on the study outcomes. Since none of the primary or secondary outcome measures were different between groups, we elected not to proceed with formal tests of mediation. Instead, we assessed for differences in family engagement and treatment initiation and adherence between groups. For each of the above sets of potential mediators, we report distributions by case/control as assess bivariate differences via t-tests or contingency tables/Chi-square analyses where appropriate.

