In order to assess family engagement, a series of items were created from review of the literature and prior instruments in other fields. We utilized confirmatory factor analyses to find distinct domains for which each item loading was greater than 0.7. Our first round of analyses resulted in 3 factors: patient/family centered care, communication, and understanding. Upon presentation to the study team, there were several items that were dropped from the initial domains, but additional items resonated with the team as important concepts in which the intervention was focused. Thus, the study team came to consensus on items that should be included. These items represented four conceptual domains. The 4factor structure was supported in confirmatory factor analyses. While the patient/family centered care and understanding domains remained the same, the original communication domain was split into two factors, resulting in the following domains: care team accessibility; patient and family-centered care; communication among members of the care team, and understanding of ADHD. To compare patients in the tier 1 and tier 2 groups by engagement status, we utilized t-tests for each of the four domains separately. Further, linear mixed effects models were implemented for each engagement domain as the outcome, with intervention status and season as covariates clustering for clinic site. We further assessed for item responsiveness using item response methods.

We explored treatment initiation and adherence via the services assessment for children and adolescents (SACA) and medication status.⁹⁵ On the SACA, patients reported service use ever, as well as service use within the past 9 months. Categorizations include any service use, ambulatory service use (any community mental health or outpatient clinic, private professional, or in-home provider), and overnight stay (psychiatric or medical unit, residential treatment center, group home, or foster home). Differences between intervention groups and treatment initiation were assessed via Chi-square tests. In addition, treatment initiation and adherence were assessed via medication status throughout the study period. At baseline and 3, 6, and 9 month follow up surveys, participants were asked as to whether their child was on or off medication. If data was missing for a particular timepoint, we utilized medication status within the EHR if available.

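### The SAP's Aim 2 medication comparison gives the collected baseline on/off status no role, so it forgoes precision and does not separate starting medication from continuing it

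*SAP*

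**What the plan says.** Protocol section 5.5 (Aim 2) treats initiation and adherence as two things. Initiation is starting a treatment plan that the family prefers at least moderately. For the other, "Adherence is defined as the continuation of treatment through month 9-12". The power statement then uses one combined rate: "Assuming that the tier 1 group of 120 children experiences a 50% rate of initiation and adherence", and "power would be about 0.89 to detect an increase in that rate among the tier 2 group to 70" per cent.

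Under Aim #2, the SAP reports that formal mediation tests were dropped and that the arms were compared on the potential mediators instead. The method for each set of mediators is to "assess bivariate differences via t-tests or contingency tables/Chi-square analyses where appropriate". For medication, the SAP says that "At baseline and 3, 6, and 9 month follow up surveys, participants were asked as to whether their child was on or off medication", with the EHR used to fill gaps where possible. It names initiation and adherence as what this status measures, but gives no rule for deciding which child initiated and which adhered. Family engagement, in the same section, also gets linear mixed models with clustering by clinic site. No model is stated for medication.

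One entry criterion in protocol section 3.4.1 is "Receiving ADHD treatment from participating practices".

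**The concern.** Starting and continuing are both defined relative to where the child began. A child already on medication at enrolment can continue or stop, but cannot start. Enrolment requires current ADHD treatment, so such children are probably common. The trial documents give no baseline share. The background in protocol section 1.3 says that 80% of treated children receive medication, but that is a literature figure.

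If the two arms are compared simply on who is on medication at follow-up, the result describes prevalence of use. It does not show whether the care manager led untreated families to begin or helped treated families to carry on. In a shared-decision trial both directions of change are possible, and they could offset each other in a prevalence comparison.

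There is also a loss of precision. Baseline status is likely to predict follow-up status strongly, and it is already collected. Leaving it out discards information that costs nothing to use. With mediation dropped, these comparisons are what remains of Aim 2 for initiation and adherence.

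**Working it through.** **Inputs from the documents.** Section 5.5 assumes "240 evaluable children parent-child dyads (from 300 enrolled" and that "these will be divided 1:1 across the two groups", so 120 per arm. The control rate is 50%, and the alternatives are 70% and 75%. The alpha level is not stated for Aim 2; two-sided 0.05 is assumed.

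**Step 1: reproduce the planned power.** The pooled two-proportion test has power Φ[(Δ − 1.96·SE0)/SE1], with SE0 = √(2p̄(1−p̄)/n) and SE1 = √((p1(1−p1)+p2(1−p2))/n).
- 50% vs 70%: p̄ = 0.60, SE0 = √(0.48/120) = 0.0632, SE1 = √(0.46/120) = 0.0619. Power = Φ[(0.20 − 0.1240)/0.0619] = Φ(1.23) = 0.890. The protocol says about 0.89.
- 50% vs 75%: the same formula gives 0.983. The protocol says greater than 0.98.
- A one-sided test would give 0.94 for 50% vs 70%, so two-sided 0.05 fits the stated figure.

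The plan's figure is therefore for an unadjusted test, and it is correct.

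**Step 2: what adjustment adds at the planned effect.** If baseline and follow-up status correlate at ρ, adjustment acts roughly like a sample of 120/(1−ρ²) per arm. The documents give no ρ, so a range is shown.

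| Assumed ρ | Effective n per arm | Power, 50% vs 70% | Power, 50% vs 65% |
|---|---|---|---|
| 0 (unadjusted) | 120 | 0.890 | 0.654 |
| 0.3 | 132 | 0.917 | 0.695 |
| 0.5 | 160 | 0.958 | 0.777 |
| 0.7 | 235 | 0.994 | 0.911 |

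**Step 3: both effects in the same direction.** Assume that staying on is 80% vs 90% and starting is 20% vs 35%. With 65% on at baseline, follow-up use is 0.65×0.80 + 0.35×0.20 = 0.590 vs 0.65×0.90 + 0.35×0.35 = 0.7075. The Step 1 formula gives 0.48. Simulation of 40,000 trials per row, 120 per arm, gives:

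| On at baseline (assumed) | Unadjusted | Mantel-Haenszel by baseline status | Continuation only | Starts only |
|---|---|---|---|---|
| 50% | 0.50 | 0.67 | 0.34 | 0.46 |
| 65% | 0.48 | 0.65 | 0.42 | 0.34 |
| 80% | 0.49 | 0.62 | 0.50 | 0.21 |
| 90% | 0.53 | 0.61 | 0.55 | 0.12 |

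Adjustment raises power in every row. Each split test has less power than the adjusted overall test.

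**Step 4: effects in opposite directions.** Assume that staying on is 85% vs 72% and starting is 20% vs 45%. With 65% on at baseline, follow-up use is 0.65×0.85 + 0.35×0.20 = 0.6225 vs 0.65×0.72 + 0.35×0.45 = 0.6255. The unadjusted and the baseline-stratified test both have power of about 0.05. The separate tests have about 0.51 (continuation) and 0.70 (starts). The near-exact cancellation depends on the assumed 65%: at 80% on at baseline the unadjusted power is 0.15, and at 90% it is 0.37.

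**Step 5: size of the split groups.** If 80% are on at baseline, 120×0.80 = 96 per arm are on and 24 are off. For 50% vs 70% within a group, power is 0.81 with 96 per arm and 0.29 with 24.

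**The case against.** The strongest reply is that nothing here falls short of the plan. The comparison was planned as an unadjusted test, its stated power is right, and randomisation makes it unbiased for current medication use. Chance imbalance in baseline medication is already allowed for in its standard error. The SAP also presents this work as exploratory. All of that stands, and it limits the point to forgone precision and unclear interpretation.

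Several stronger readings are tempting, and the documents do not support them:
- **That the SAP never uses baseline medication status.** Medication status is a covariate in the Aim #1 models and a moderator in Aim #3, with the time point not stated. The gap concerns the Aim 2 comparison only, and it is inferred from silence there.
- **That starts and stops were certainly pooled.** The Chi-square sentence in the initiation and adherence text follows the SACA categories. The general bivariate wording would also allow a table of transition categories. What can be said is that no such rule is stated.
- **That failing to separate starting from continuing loses power.** The gain comes from baseline adjustment. When effects run the same way, each split estimate has less power than the adjusted overall test.
- **That an off-to-on and on-to-on split would deliver the protocol's own outcomes.** Section 5.5 ties initiation to treatment preference, through the ADHD PGI, and defines adherence by treatment, not medication alone. A child who moves from medication to a preferred behavioural treatment would be misclassified.

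**Conclusion.** The point holds in a limited form. For the Aim 2 arm comparison of medication, the stated method is bivariate, the collected baseline status has no stated role, and nothing separates starting from continuing.

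The cost in precision depends on quantities that the documents do not give. For assumed correlations of 0.3 to 0.7, adjustment would raise power from 0.89 to between 0.92 and 0.99 at 50% vs 70%, and from 0.65 to between 0.70 and 0.91 at 50% vs 65%. In the same-direction scenario, with 50% to 90% on medication at baseline, it rises from 0.48–0.53 to 0.61–0.67.

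The interpretive gap matters at least as much. An overall on/off result, adjusted or not, does not say whether the care manager affected initiation, continuation or both. A reader might infer that the comparison is biased or underpowered against the plan; it is neither. The primary and secondary outcome comparisons do not depend on it. The improvement is worth making because the data are already held.

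**What to change.** In the SAP's Aim #2 text on initiation and adherence:

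1. Replace the bivariate medication test with an analysis of on-medication status at 3, 6 and 9 months by logistic GEE (or Mantel-Haenszel), with arm and baseline on/off status, accounting for clinic site as the other models do.
2. Report separately, with denominators and as descriptive, medication starts among children off at baseline and medication continuation among children on at baseline. State the rule that turns the four reports into each category.
3. Label both as medication-based approximations of the section 5.5 definitions, which also involve treatment preference and non-drug treatment.
4. Describe the SACA past-9-month result as service use. Protocol section 4.5.1 times the SACA at 9-12 months only, and its ever-used and past-9-month items cannot show that use began after randomisation.

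The cost is SAP wording and a short re-analysis. The adjusted overall comparison has essentially no downside, but it does not detect offsetting effects; the split estimates are there to show those. They rest on small groups, about 24 per arm off medication if 80% are on at baseline, so they should carry confidence intervals and no confirmatory claim.
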